#### 4.2.7. Subgroup analysis for the primary outcome

We pre-specified in the original protocol three subgroups, as follows:

- 1) Type of admission (medical vs. surgical),
- 2) Tertiles of SAPS3 and
- 3) Mechanical ventilation status (invasive MV vs. not-invasive MV).

We now revised their definition for clarification and added three additional subgroups, based on the main research question of the trial and the literature. Thus, the final six subgroups are defined below:

- 1) Type of ICU admission (3 categories: medical, elective surgical, unplanned surgical)
- 2) Tertiles of SAPS 3 score (defined by “ntile(SAPS3,3)”)
- 3) Invasive mechanical ventilation at ICU admission (2 categories: yes, receive invasive mechanical ventilation at ICU admission; no, receive other respiratory support rather than invasive mechanical ventilation or none)
- 4) Age groups (3 categories: 18-39 years, 40-59 years, 60+ years)

- 5) ICU performance in the baseline (4 categories: most efficient, least efficient, overachieving, underachieving)
- 6) Calendar time from the intervention in trimesters (as categorical)

Sub-groups will be analyzed adding an interaction term between the  $X_{ij}$  in Equation (1) and the subgroup of interest, and a term for the fixed effect of the subgroup of interest if it is not already a covariate. The p-value for the interaction will be evaluated by a likelihood ratio test comparing the model without the interaction and with the interaction.

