## 2.6. Power calculation

### 2.6.1. Original power calculation

Prior to the start of the trial and baseline period, for the funding application, we estimated a mean ICU length-of-stay of 8 [standard deviation (SD) 10] days for general adult public ICUs in Brazil. We used data from published literature and reports from the online project “UTIs Brasileiras”. In 2018, the “UTIs Brasileiras” dashboard had data of ICU LOS from 242 public ICUs in Brazil (n=3,199 beds). Using data from 20 ICUs (10 ICUs from [name] et al, 10 ICUs from the ORCHESTRA study, available in the *ems* R package), we estimated an intraclass correlation coefficient (ICC) of 0.018. Considering a two-arm cluster trial with an ICC of 0.018, for a minimum difference of an average length of stay of 1.5 days (8.0 to 6.5 days)

and SD of 10 days, power 80%, alpha 5%, we would need a total of 30 clusters (15 intervention units and 15 control units) with an average cluster size of 500 patients per ICU over a period of 18 months. Cluster size can vary and if the cluster size variation is high, usually measured by the coefficient of variation (CV), the power of the trial decreases. We estimated the CV using the expected minimum and maximum method of the cluster size: assuming a minimum cluster size of 350 patients and maximum of 650 patients (i.e., range 300, approximated SD of 75), for a mean size of 500 patients, we would have an approximated CV of 0.15 and maintain 80% power.

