#### 4.2. Statistical analyses

We will follow the framework proposed in the literature to optimize the power and properly account for time in cluster parallel randomized trials with baseline period (longitudinal cross-sectional cluster trials). Thus, we will consider the baseline individual data allowing the secular trend to vary randomly across clusters by extending the random-effects components with an interaction between cluster and time period (baseline vs after randomization). This term also allows for the ICC to differ from observations that are made in the same or different time periods and for estimating two ICCs (the “within-period ICC” and the “between-period ICC”) used to estimate the CAC (the ratio of the between-period and within-period ICCs).

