#### 4.2.4. Analysis of secondary outcomes at ICU level

The main outcome at the ICU level is the ICU performance classification. The performance will be defined in the baseline and after intervention periods without considering if the unit is in the intervention or control group. Thus, we will estimate if there will be a shift towards better performance for the ICUs in the intervention group, i.e., if there will be more commonly “most efficient” and “overachieving” ICUs in the intervention group.

Based on the background that the intervention might be more efficient overtime, in an exploratory analysis we will analyze the ICU performance classification at the last 3 months of the intervention.

For the ICU level outcomes, we will include all patients who fulfilled all inclusion criteria and none exclusion criteria, and we will include readmissions.

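### The arm-by-trimester test for the primary outcome (subgroup 6) has no ICU-by-trimester random term, so its p-value is too small if ICU means drift during follow-up

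*SAP*

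**What the plan says.** SAP 4.2.7 adds three subgroups to the three in the original protocol. The sixth on the final list is "Calendar time from the intervention in trimesters (as categorical". I read it as time since the ICU entered its intervention or control period, cut into three-month categories. For every subgroup the model is Equation (1) plus an interaction with arm and, where it is not already there, a fixed main effect. The test is stated as: "The p-value for the interaction will be evaluated by a likelihood ratio test comparing the model without the interaction and with the interaction".

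The random part of Equation (1) is described in SAP 4.2 as "extending the random-effects components with an interaction between cluster and time period (baseline vs after randomization". SAP 4.2.1 codes the period as 0 or 1, so there is a single ICU-by-period effect for the whole of follow-up. The same section adopts the Satterthwaite correction for the primary outcome; 4.2.7 does not carry it over.

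SAP 4.2.4 gives the motive for looking at time: "Based on the background that the intervention might be more efficient overtime". It then plans an exploratory look at ICU performance classes in the last three months. SAP 5.1.6 adds descriptive three-monthly series. Subgroup 6 is the only formal test of a changing effect on the primary outcome.

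**The concern.** Treatment was allocated to 30 ICUs, so a change in its effect over time has to be judged against how much ICU means move over time without any change in effect. The subgroup 6 model has no term for that movement. It represents drift between baseline and follow-up but assumes none between trimesters within follow-up.

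The SAP does not otherwise suppose that ICUs are stable. SAP 4.2 lets the secular trend differ at random between ICUs. SAP 4.1.5 says the pandemic probably altered the patients admitted and that units could become COVID-19 or non-COVID-19 reference centres after randomization, with no adjustment for this.

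At stake is the interaction p-value that SAP 5.1.5 will print on the forest plot. A small value could be read as tele-rounds needing time to work, or wearing off, when it reflects ordinary ICU-level drift. Since the SAP already expects efficiency to grow with time, such a result would be readily believed.

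**Working it through.** **Why the random effect drops out.** Write u_i for the ICU effect and v_i1 for the ICU's post-randomization effect. The mean of ICU i in trimester t is the fixed part + u_i + v_i1 + the mean of its patients' errors. A difference between two trimesters of the same ICU removes both u_i and v_i1. In the fitted model only patient error remains, so the likelihood ratio test uses that alone as its yardstick for arm by trimester.

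**Inputs from the SAP.** The original design (2.6.1) is stated as "SD of 10 days, power 80%, alpha 5%, we would need a total of 30 clusters", with a "minimum difference of an average length of stay of 1.5 days (8.0 to 6.5 days" and an "average cluster size of 500 patients per ICU over a period of 18 months"; also "we estimated an intraclass correlation coefficient (ICC) of 0.018". After baseline (2.6.2): unadjusted ICC 0.087, SD 9.8, coefficient of variation (CV) of cluster size 0.4, 80% power kept down to a cluster autocorrelation (CAC) of 0.906, and CAC estimates above 0.960 in the 20 reference ICUs.

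**The plan's own figures first.** The SAP states no error rate for the subgroup test, only power.
- Original: design effect 1 + 499 × 0.018 = 9.982; standard error 10 × √(2 × 9.982 / 7500) = 0.516; 1.5 / 0.516 = 2.91. Power is 80.1% (t, 28 df) or 82.8% (normal).
- Revised: M = 500 × (1 + 0.4²) = 580; 1 + 579 × 0.087 = 51.37; r = 580 × 0.087 × 0.906 / 51.37 = 0.890; design effect 51.37 × (1 − r²) = 10.7. Power is 80.2% (SD 10, normal), 81.8% (SD 9.8, normal) or 79.0% (SD 9.8, t).

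Both agree with 80%, so the inputs are being read as the SAP means them.

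**Error rate of the planned test.** Assumptions: 18 months as six trimesters, so 500 / 6 = 83.3 patients per ICU per trimester; equal cluster sizes; the same correlation c between any two trimesters of an ICU; ICC on the analysed log scale as shown. With total variance 1, the true variance of a trimester mean in the contrast, divided by the variance the model assumes, is

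k = 1 + ICC(1 − c) / [(1 − ICC) / 83.3],

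and the rejection rate of the nominal 5% test is P(χ² on 5 df > 11.07 / k).

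Example, ICC 0.087 and c = 0.96: k = 1 + 0.00348 / 0.01096 = 1.32; 11.07 / 1.32 = 8.40; rate 13.5%.

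| ICC | c | k | Rejection rate |
|---|---|---|---|
| any | 1 (no drift) | 1.00 | 5.0% |
| 0.087 (unadjusted) | 0.98 | 1.16 | 8.9% |
| 0.087 | 0.96 | 1.32 | 13.5% |
| 0.05 (assumed) | 0.96 | 1.18 | 9.3% |
| 0.03 (assumed) | 0.96 | 1.10 | 7.4% |
| 0.087 | 0.906 | 1.75 | 27.5% |

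**Check by simulation.** Null trials were fitted by maximum likelihood with Equation (1), trimester and block effects: 30 ICUs in blocks of 14, 7 and 9, CV 0.4, ICC 0.087, no patient covariates, assumed arm splits 7/7, 4/3 and 4/5, and 2000 trials per scenario. The planned test rejected in 4.9% with no trimester drift, 8.8% at c = 0.98, 14.9% at 0.96 and 31% at 0.906. The no-drift result points to the missing random term, not the likelihood ratio test alone, as the cause of the excess.

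Adding a random ICU-by-trimester term after randomization brought the same likelihood ratio test to 5.6%, 7.1% and 7.8% at those three correlations.

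**The case against.** The strongest reply is that all of this is conditional, and that is right. The SAP's CAC compares baseline with follow-up, not one trimester with another. With no drift inside follow-up the planned test holds its level. The ICC of 0.087 is unadjusted, while the analysis adjusts for SAPS-3, admission type and invasive ventilation (4.2.6), and 2.6.2 itself expects adjustment to lower the ICC. Part of any case-mix drift would be absorbed in this way.

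Four stronger readings are tempting and should be resisted.
- That this is the SAP's only analysis of length of exposure. SAP 4.2.4 plans another, at ICU level.
- That the test will reject far too often. The documents do not establish how much ICU means drift.
- That 27.5% is what the SAP's figures predict. In 2.6.2 the value 0.906 is where power falls to 80%, not an estimate; the estimates exceeded 0.960.
- That the SAP's own CAC implies a rate near 30%. Simulation gives 30% when 0.96 is the correlation of adjacent trimesters and decays with distance. Averaged over six trimesters, with baseline as one preceding trimester, that decay gives a baseline-to-follow-up correlation of about 0.90, below what 2.6.2 reports.

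It can also be said that subgroups are exploratory (4.1.4). That limits the consequence, but the label there concerns multiple comparisons. It does not make a single p-value valid when its yardstick leaves out the relevant variation.

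**Conclusion.** The point stands in conditional form. As specified, subgroup 6 tests arm by trimester against patient-level error only, so its p-value is too small whenever ICU means drift between trimesters. SAP 4.1.5 gives good reason to expect some drift.

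A reasonable range for the true level of the nominal 5% test is 5% with no drift, about 7-9% at correlation 0.96 with an assumed adjusted ICC of 0.03-0.05, and about 9% and 14% at correlations 0.98 and 0.96 with the unadjusted ICC. Lower or decaying correlation would take it higher. These figures rest on exchangeable correlation, 83 patients per ICU per trimester and 5 df. The randomization dates in 2.4 imply unequal follow-up across blocks, so six equal trimesters is a simplification.

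The primary estimate and its test are not touched. The damage is confined to one exploratory subgroup result, and it is cheap to prevent.

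**What to change.** Add to SAP 4.2.7 that, for subgroup 6 only, Equation (1) gains an ICU-by-trimester random intercept, with baseline as its own level, and that arm by trimester is tested with an F test using the Satterthwaite correction already chosen in 4.2.1, in place of the likelihood ratio test.

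The corrected test matters as well as the random term. With the term added, the likelihood ratio test still rejected in 5.6-7.8% of null trials under exchangeable correlation at 0.906 to 0.98, and in 8-11% under decay, partly because the number of ICUs is small. The F test itself was not simulated here.

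The cost is a sentence in the SAP, one more variance component in an exploratory model, and a somewhat wider interval for each trimester.

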### 2.5.2. Secondary exploratory outcomes

The secondary outcomes of this study include assessing the impact of interventions implemented through Telemedicine compared with a control group in the following outcomes:

At the unit level:

- Classification of the unit according to the profiles defined by the SRU and the SMR. The SRU reflects the observed / expected rate of resources used (estimated as ICU length of stay for surviving patients), adjusted by the patient's severity of illness (SAPS 3).

The SMR reflects the observed / expected rate (according to severity score) of hospital deaths. The profiles are a combination of SMR (above or below median) and SRU (above or below median): Each unit can be assigned to one of the four groups:

"most efficient" (SMR and SRU < median); "least efficient" (SMR, SRU > median);

"overachieving" (low SMR, high SRU), "underachieving" (high SMR, low SRU).

At an individual level:

- In-hospital mortality, defined as death by any cause, within the period from the date of ICU admission to the date of hospital discharge or death, whichever comes first.
- Incidence of central line-associated bloodstream infection (CLABSI), as defined by the CDC.
- Incidence of ventilator-associated event (VAE), as defined by the CDC.
- Incidence of catheter-associated urinary tract infection (CAUTI), as defined by the CDC.
- Ventilator-free days at 28 days, defined as the number of days from successfully weaning to day 28; patients who died before weaning were deemed to have no ventilator-free days
- Rate of patients receiving oral or enteral feeding, defined as any amount of oral or enteral diet, during ICU stay
- Rate of patients under light sedation or alert and calm [Richmond Agitation-Sedation Scale (RASS) = -3 to +1]
- Rate of patients under normoxemia [peripheral oxygen saturation (SpO2) between 92% and 96%]

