## 4. Statistical methods analysis

### 4.1. General analysis issues

#### 4.1.1. Analysis population

Primary statistical analyses will be performed according to the intention-to-treat principle. Patient outcomes will be analyzed according to the randomization of the ICU each patient was in, regardless of whether or not the intervention was applied in that ICU. The baseline period is defined as the first two months of data collection in each ICU. The period for the evaluation of the intervention will be defined as the day after the randomization, thus patients admitted to the ICUs the next day of randomization are accounted as of the intervention/control period. Primary statistical analysis will also consider the baseline period in the analyses, while patients admitted to some of the ICUs during the “Interstitial” period (between baseline and randomization) will be excluded.

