##### 4.2.1. Analysis of the primary outcome

The linear mixed model for the primary outcome will be the following:

$$Y_{ijk} = \beta_0 + \beta_1 X_{ij} + \beta_2 j + \beta_3 Z_{ijk} + \beta_4 L_{ij} + \mu_i + \nu_{ij} + \epsilon_{ijk} \quad \text{Equation (1)}$$

for cluster  $i$ , time-period  $j$  and participant  $k$ , where  $X_i$  denotes the trial arm for cluster  $i$  (coded 0 or 1), and  $j$  denotes the time-period in which participant  $k$  in cluster  $i$  is assessed (0 for baseline, 1 for after randomization). The individual error term is assumed to be Normally distributed and independent of  $\nu_{ij}$  and  $\mu_i$ . Random terms are assumed to be Normally distributed, and  $\nu_{ij}$  is assumed independent of  $\mu_i$ .  $Z_{ijk}$  and  $L_{ij}$  are the matrix of covariates at the individual level and unit level, respectively.  $\beta_1$  is the coefficient of interest for the trial, i.e., the estimate for the difference between those receiving the intervention and those in the control group.

For the primary outcome, we will include the index admission of a patient, i.e., we will not include ICU readmissions. The primary outcome – ICU LOS – will be log-transformed to account for the normality of the residuals of the linear mixed model. These two steps (not including readmissions and log-transformation) were used for the power calculations.

We will use the identity link in the model for the primary outcome and the Satterthwaite's degree-of-freedom correction.

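### Subgroup 5 (baseline ICU performance): the interaction model omits class-by-period, so regression to the mean can enter the contrast, and its uncorrected likelihood ratio test on 30 ICUs over-rejects

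*SAP*

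**What the plan says.** - **Subgroup model (SAP 4.2.7).** Each subgroup is interacted with X in Equation (1), "and a term for the fixed effect of the subgroup of interest if it is not already a covariate". Baseline ICU performance (four classes) is subgroup 5 and also covariate 6 in SAP 4.2.6. Nothing beyond X-by-class is therefore added for it.
- **Test (SAP 4.2.7).** "The p-value for the interaction will be evaluated by a likelihood ratio test comparing the model without the interaction and with the interaction". No reference distribution or small-sample correction is named. For the primary model, SAP 4.2.1 names Satterthwaite's "degree-of-freedom correction".
- **Meaning of X (SAP 4.2.1).** Equation (1) carries X with subscripts for cluster and period. The text below it says that X "denotes the trial arm for cluster" i, and calls its coefficient "the estimate for the difference between those receiving the intervention and those in the control group".
- **Baseline data are responses.** SAP 4.1.1: "Primary statistical analysis will also consider the baseline period in the analyses". SAP 4.2 does this by "extending the random-effects components with an interaction between cluster and time period". Equation (1) has one fixed period coefficient for all ICUs.
- **How class is built (SAP 2.5.2).** ICUs are split at the medians of SMR and SRU. "The SRU reflects the observed / expected rate of resources used (estimated as ICU length of stay for surviving patients", with adjustment for severity.
- **Status.** SAP 4.1.4 labels subgroup analyses exploratory and unadjusted. SAP 5.1.5 prints the interaction p-value on the forest plot.

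**The concern.** There are two separate problems, both confined to subgroup 5.

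**Bias, on one reading of X.** Suppose X is 1 only for intervention ICUs after randomization. Every observation with X = 1 is then post-randomization, and X-by-class is the only term that lets classes change differently over time. ICUs put in a high-SRU class partly because of chance or transient baseline LOS will tend to fall afterwards in both arms, and low-SRU ICUs will tend to rise. The random cluster-by-period effect has mean zero and cannot absorb a shift tied to class. Part of the shift therefore appears as effect modification: the intervention looks better in high-SRU ICUs and worse in low-SRU ICUs.

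**Test size, on either reading.** Arm and class are both ICU-level factors, so the 3-df interaction is judged on 30 ICUs, about four per arm-by-class cell. A likelihood ratio statistic referred to chi-square, the usual default, is too liberal with so few units.

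At stake are one forest-plot panel and its p-value.

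**Working it through.** **Inputs from the SAP.** 30 ICUs, 15 per arm; 500 patients per ICU over 18 months; mean 8, SD 10 days; original ICC 0.018 (2.6.1). Baseline ICC 0.087, cluster-size CV 0.4, CAC threshold 0.906, estimated CAC above 0.960 (2.6.2). Two-month baseline (4.1.1).

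**Assumed or derived.** Baseline patients per ICU: 500 × 2/18 ≈ 56. Log-SD: √ln(1 + (10/8)²) = 0.97. ICC 0.087 is carried to log LOS, SMR is independent of LOS, and severity is taken as fully adjusted. For the survivor-based class, 70% are survivors (the SAP gives no mortality).

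**1. The plan's own figure.** The SAP states no error rate for the subgroup test, so its power is the available check. Design effect 1 + 499 × 0.018 = 9.982; SE = √(2 × 100 × 9.982 / 7,500) = 0.516; 1.5/0.516 = 2.91. On 28 df, power is 80.1% (79.3% with CV 0.15). The stated 80% reproduces.

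**2. How much regression to expect (X as arm-by-post).** In units of total variance, a baseline ICU mean has variance 0.087 + 0.913 × (1 + 0.4²)/55.6 = 0.106. The share of its deviation that carries over is CAC × 0.087/0.106, i.e. 0.79 (CAC 0.96) or 0.74 (CAC 0.906). A median split on this mean separates the halves by 2 × 0.798 × √0.106 = 0.52 SD. The expected null shift between periods is 0.52 × (1 - 0.788) = 0.11 SD, or 0.107 log-days (0.129 at CAC 0.906). This is the most that could load on X-by-class when class is split on baseline mean log LOS itself. With 500 baseline patients it is 0.029 log-days (CAC 0.96).

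**3. Null simulations, X as arm-by-post.** No treatment effect and no effect modification; restricted allocation; covariates class, beds, region and block; nominal 5%; about 2,000 trials per setting; 56 baseline patients unless stated. Paired values are CAC 0.96 / 0.906.

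| Correlation of SRU with baseline mean log LOS | High-minus-low SRU contrast, log-days | LRT as written | LRT with class-by-period |
|---|---|---|---|
| Survivor-based class (0.89) | -0.074 / -0.090 | 17.4% / 17.6% | 17% / 18% |
| 0.7 | -0.063 / -0.075 | 12.8% / 15.6% | 13% / 15% |
| 0.5 | -0.043 / -0.054 | 11.3% / 13.3% | 12% / 14% |
| 1.0 | -0.080 / -0.094 | 20.4% / 21.0% | 18% / 20% |
| Unrelated | 0 | 8.8% / 8.7% | 10% / 13% |
| Survivor-based, 500 baseline patients (CAC 0.96) | -0.024 | 10.9% | 15.3% |

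For the survivor-based class, half of the contrast each way gives spurious LOS ratios of exp(0.037) to exp(0.045), i.e. 1.04-1.05, in low-SRU ICUs and about 0.96 in high-SRU ICUs. The design difference is 1.5/8.0 = 19%.

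**4. Which part of the excess is small-sample error.** In a second set (3,000 trials per setting, correlation 0.8), the LRT as written rejected 14.1% / 16.1%. Changing only the test to a REML F test gave 8.5% / 9.4%, which removes 5.6 of 9.1 and 6.7 of 11.1 excess points. Adding class-by-period and using the F test on (3, 22) df gave 6.1% / 6.7%. Adding class-by-period while keeping the LRT gave 14.8% / 16.8%. Over all settings with class linked to LOS, class-by-period plus the F test rejected 5.1-7.7%, and the spurious contrast fell to about 0 (-0.004 to +0.003 SD).

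**5. X as arm.** The size can be checked without simulation. ICU-level parameters: intercept, arm, class (3), arm-by-class (3), beds, region, block (2) = 12, leaving 18 df. The LRT exceeds 7.815 when F > (exp(7.815/30) - 1) × 18/3 = 1.785, and P(F(3,18) > 1.785) = 18.6%. The 5% cutoff is 3.16. Simulation gives 18-20%, with no detectable bias; a REML F test on (3, 18) df gives 5.0-5.8%.

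**The case against.** **One exploratory subgroup, small effect.** This stands and sets the weight of the point. The exploratory label waives multiplicity adjustment, but it does not make a single printed p-value valid.

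**The bias depends on a notation the SAP does not settle.** This also stands. The text defines X as arm, and then there is no bias. But X-by-class would then pool baseline and post-randomization patients, and would not measure modification of the treatment effect. That is why X must be defined first.

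**The sizes rest on assumptions.** True for the size of the bias, which shrinks to -0.024 with 500 baseline patients. That figure is the power calculation's simplification, which SAP 2.6.2 itself flags, and not a two-month count. The direction of the bias and the over-rejection did not depend on these choices.

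**Stronger readings a reader might infer:**

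- *The primary result is compromised.* Not supported. In null simulations the primary estimate was unbiased (0.001 / 0.003). The size of the primary test was 6.3-6.9% in approximate models that treat the residual variance as known. That neither shows a defect nor clears the test, so the claim here is only that the primary estimate is not biased by this point.
- *Interval coverage for the contrast is only 80%.* That holds only for ML standard errors with a normal quantile. With REML and t intervals, closer to the correction in SAP 4.2.1, coverage is about 84-86% as written and 94-95% with class-by-period.
- *The other subgroups share the fault.* Nothing here was shown for subgroups 1-4 or 6.

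**Conclusion.** The point holds as a minor correction to exploratory subgroup 5.

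- **X as arm-by-post:** the planned model yields a spurious high-minus-low SRU contrast of about -0.07 to -0.09 log-days with about 56 baseline patients per ICU and a survivor-based class. It is -0.04 to -0.05 at a correlation of 0.5, and about -0.02 with 500 baseline patients (CAC 0.96). It is absent if class is unrelated to baseline LOS.
- **X as arm:** this bias is absent.
- **Test size, nominal 5%:** about 11-21% with X as arm-by-post and class linked to baseline LOS (about 10-11% with 500 baseline patients), about 9% if unlinked, and about 19% with X as arm.
- **Source of the excess:** mostly small-sample error, in the sense that changing the test alone removes more than half of it. With X as arm-by-post, the remainder comes from deriving class from LOS data that are also responses.

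The main assumptions are the baseline count, the SRU-LOS correlation, ICC 0.087 on the log scale, independence of SMR from LOS, and a chi-square reference for the LRT.

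**What to change.** 1. In SAP 4.2.1, state that X is 1 only for intervention ICUs after randomization and 0 otherwise.
2. In SAP 4.2.7, for subgroup 5 only, put class-by-period in both compared models and replace the chi-square LRT with a REML F test on ICU-level degrees of freedom (about 5-8% rejection). Both changes are needed: class-by-period alone removes the bias but leaves the LRT at about 10-20%.
3. Acceptable alternative or sensitivity check: an ICU-level ANCOVA F test of post-randomization mean log LOS on baseline mean, arm, class and arm-by-class (about 4-6%). SAP 4.2.3.2 already carries baseline LOS as a unit-level mean. This option gives up the patient-level covariates of SAP 4.2.6.

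**Cost.** Wording and one replaced test; SAP section 1 says no analysis has yet been done. For the survivor-based class, the SD of the contrast rises from 0.086 / 0.096 to 0.118 / 0.135 with class-by-period, or to 0.114 / 0.131 with ANCOVA, overall about 32-40%. RMSE does not improve: 0.113 / 0.132 as written, 0.118 / 0.135 with class-by-period, 0.114 / 0.131 with ANCOVA. The gain is an unbiased contrast and near-nominal error rates, not accuracy. Power stays low: 25% / 21% with ANCOVA even if the whole design effect fell in high-SRU ICUs alone.
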